## 3.3 Sample size

The sample size is calculated with a projected rate of composite event of failure at 12 months of 15% in the group "TIPS" [estimated from Garcia Pagan, New Engl J Med 2010] versus 40% in the group « glue» [estimated from Hou, Gastrointest Endosc 2009].

A number of 52 patients in each group will achieve 80% power to detect TIPS superiority using a one-sided logrank test at a 0,050 significance level, with a proportion dropping out of both groups of 10%.

Total number of scheduled patients recruited or observations collected: 104.

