## **Primary composite endpoint**

The Kaplan Meier method will be used to estimate rate of composite event over the 12-month follow-up. The composite event rates will be compared between study arms using the log-rank test. Hazard ratio for composite event rate (TIPS vs. GO) and its 95% confidence interval will be determined using a Cox proportional hazard model. In this model, a center effect will be tested as well as interaction between treatment and center. The assumption of proportional hazards will be tested using Schoenfeld residuals and if violated, the model will be fitted with a treatment-time interaction or a time-varying covariate, as appropriate.

The composite event rate at 12 months will be described according to a number of covariates including age, gender, and specific liver scores (Child-Pugh and MELD) to examine their potential effects. Each of these factors will be analyzed statistically using a Cox proportional hazard model incorporating terms for treatment strategy, the covariate and the strategy-by covariate interaction. The number of patients with composite event, estimated hazard ratios, and associated 95% confidence intervals will be calculated within each of the subgroups generated by these analyses.

Covariate			Treatment effect	P
	n	No. Events	HR - 95%CI	value
Intervention				р
Glue			Ref	
obliteration				
Early			Treatment effect	
TIPS				
Subgroup analyses				
Age				P*
<median< td="">		<median effect<="" td="">	</median>	</median<>			<median effect<="" td="">	</median>	

>median			>median effect	
Sex				P*
Male			Effect in men	
Female			Effect in women	
Child Pugh				P*
score				
В			Effect in B patients	
С			Effect in C patients	
MELD				P*
<median< td="">		<median effect<="" td="">	</median>	</median<>			<median effect<="" td="">	</median>	
>median			>median effect	
EH upon adm	niss	on		
No				
Yes				
High risk pat	ient	s (Child-Pugh	C, or Child-Pugh B with active bleeding)	
Not high			Effect in not high-risk patients	
risk				
High risk			Effect in high-risk patients	
Shock				P*
No shock			Effect in patients with shock	
Shock			Effect in patients without shock	
ACLF upon a	adm	ission†		P*
Grade 1				_
Grade 2				_
Grade 3				
Red blood cell transfusion during initial hospitalization				P*
0	)		Effect in untransfused patients	
1-2			Effect in transfused patients 1-2 RBC units	
>2			Effect in transfused patients with more than RBC units	

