\* p value for interaction

The win ratio method (Pocock et al. Eur Heart J. 2012 Jan;33(2):176-82) will also be applied in order to determine the least effective procedure when giving priority to the more clinically important event (death).

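### The subgroup table appears to test effect modification by age and MELD on a sample-median split, which costs information in interaction tests that are already weak

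*SAP*

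**What the plan says.** SAP section 6.2, under the primary composite endpoint, describes the 12-month event rate by "covariates including age, gender, and specific liver scores (Child-Pugh and MELD) to examine their potential effects". Each factor goes into a Cox model "incorporating terms for treatment strategy, the covariate and the strategy-by covariate interaction". That sentence does not say whether age and MELD are continuous or categorised.

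The next sentence says that patient counts with events, hazard ratios and confidence intervals "will be calculated within each of the subgroups generated by these analyses".

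In the table shell, age and MELD each have two rows, below and above the median (the second is labelled ">median effect"). The starred P stands on the covariate's header row, and the footnote defines it as the "p value for interaction". No row, footnote or sentence provides for a continuous interaction term.

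Both variables are numeric elsewhere in the SAP. Age has numeric limits in section 5.1. MELD is listed among the baseline scores in section 5.3, and its change to Day 180 is a secondary endpoint compared by t-test or Mann-Whitney test.

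**The concern.** Splitting a numeric modifier at its median treats everyone within a half as alike and patients just either side of the cut as different. If the effect of TIPS changes gradually with MELD or age, the spread within each half carries information on that change, and the split discards it.

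Whether the benefit depends on liver severity is a natural question for this trial, and MELD is one of the ways the table asks it. The trial expects few events, so the interaction tests have little information to spare.

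There are two smaller points. The cut value is not known until the data are in, so hazard ratios by half are hard to set beside those of another trial. The labels are strictly below and strictly above the median, so a patient exactly at the median belongs to neither row. This will matter if ages or scores are recorded as whole numbers with ties.

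**Working it through.** **Inputs from the SAP.** Section 3.3: 52 per arm, 12-month event rates of 15% (TIPS) and 40% (glue), 80% power, "one-sided logrank test at a 0,050 significance level", 10% dropout. Section 4.1: tests two-sided at 0.05, which is applied to the interaction tests below.

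**Inputs assumed.** The shape of the modifier's distribution and a log-linear interaction. The SAP gives neither.

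**Step 1. The plan's own figure.** The SAP states no figure for the split, so the only one to reproduce is the sample size. Schoenfeld's formula with the hazard ratio taken as the ratio of risks, 0.15/0.40 = 0.375:

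- Events = 4 × (1.645 + 0.842)² / (ln 0.375)² = 25.7, so 26.
- Per arm before dropout = 26 / (0.15 + 0.40) = 47.3.
- With 10% dropout: 47.3 × 1.10 = 52.0, or 47.3 / 0.90 = 52.5.

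The stated 52 per arm is reproduced.

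**Step 2. Expected events.** If the 10% who drop out contribute nothing, 46.8 per arm remain and 46.8 × 0.55 = 25.7 events are expected. If dropout occurs at a constant rate over the year, the figure is 27.2. Hence about 26 to 27.

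**Step 3. Information kept by a median split.** For a log-linear interaction, the efficiency of the split relative to the continuous term is approximately the squared correlation between X and the indicator that X exceeds its median. For a standard normal X:

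- Covariance = 1/√(2π) = 0.399; SD of the indicator = 0.5.
- Correlation = 0.399 / 0.5 = 0.798; squared = 2/π = 0.637.
- Loss = 1 − 0.637 = 36%.

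So 25.7 events inform the interaction about as well as 25.7 × 0.637 = 16.4 would with the continuous term. On the patient scale, 104 × 0.637 = 66.

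| Assumed shape of the modifier | Information lost |
|---|---|
| Uniform | 25% |
| Normal, mean 57, SD 10, cut to 18–75 years | 34% |
| Normal | 36% |
| Gamma, shape 4 | 41% |
| Lognormal, sigma 0.4 | 44% |
| Exponential | 52% |

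**Step 4. How weak the split test is.** Ignoring any prognostic effect of the modifier, the TIPS arm expects 46.8 × 0.15 = 7.0 events, or 3.5 per half. The glue arm expects 46.8 × 0.40 = 18.7, or 9.4 per half. The standard error of the log ratio of the two hazard ratios is about √(2/3.51 + 2/9.36) = 0.885. An observed ratio between the halves would need to reach about exp(1.96 × 0.885) = 5.7 for two-sided p < 0.05.

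**Step 5. Power by simulation.** N = 104, the SAP's event rates and dropout, normal modifier, log-linear interaction, two-sided 5%:

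| Interaction HR per SD | Test | Continuous | Split |
|---|---|---|---|
| 1.49 | likelihood ratio | 15% | 13% |
| 1.49 | Wald | 14–15% | 4–6% |
| 2.23 | likelihood ratio | 48% | 33% |
| 2.23 | Wald | 46–48% | 12–17% |

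The Wald ranges cover runs without and with a prognostic effect of the modifier; the likelihood-ratio rows are without one. With no interaction, the Wald test on the split rejected in about 3% of runs and the continuous tests in about 5–6%. The Wald gap is larger because the split sometimes leaves a TIPS half with almost no events, where the Wald test breaks down. With the larger interaction, a TIPS half had no events at all in roughly one run in ten. The likelihood-ratio gap is the fairer measure of what the coding itself costs.

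**The case against.** **The text does not say that the interaction is tested on the split.** The model sentence fits a continuous covariate equally well. A blank table with the p value on the header row and hazard ratios by half is compatible with a continuous test and a split display. This stands as a limit: the point is an inference from the table shell and from the sentence tying the hazard ratios to the subgroups these analyses generate. It does not remove the point. If a continuous term was intended, the SAP still leaves open which model yields the p value, and the same sentence settles it.

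**A reader might infer that a third of the information is lost whatever the data look like.** The documents do not support that. They give no distribution for age or MELD and no form of interaction, so 36% is conditional and must be read with the 25% to 52% range.

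**A reader might infer that a cut taken from the data opens the way to false positives.** It does not. The median is a rule fixed in advance, applied to a baseline variable and blind to outcome. The simulated Wald test on the split rejected less often than 5% when there was no interaction.

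**The split has one advantage.** It needs no linearity assumption, and about 26 events could hardly check one. The power comparison above assumes the log-linear setting that favours the continuous term. This stands.

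**The stakes are modest.** The SAP presents these as analyses of potential covariate effects. Severity is also examined through Child-Pugh class, a high-risk group, ACLF grade and shock, none of which is cut at a sample median.

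**Conclusion.** The point holds as a cheap improvement to subgroup analyses. The table shell attaches the interaction p value for age and MELD to below-median and above-median rows and the text specifies no continuous term, so the interaction appears to be tested on the split. Under a normal modifier and a log-linear interaction this loses 36% of the information on the interaction; across the other shapes tried it loses 25% to 52%. All of these figures rest on assumptions that the SAP does not supply.

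Two stronger conclusions should not be drawn. The primary log-rank test, the main hazard ratio and the sample size do not depend on this coding. Nor would continuous coding make the interaction tests adequate: even for an interaction hazard ratio of 2.23 per SD, simulated power stayed below 50%. The change reduces an avoidable loss, and the results remain exploratory.

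**What to change.** Add to SAP section 6.2 that the interaction p value for age and for MELD comes from the Cox treatment-by-covariate term with the covariate entered as continuous (linear). Report the treatment hazard ratio with its 95% CI from that model at, for example, the 25th, 50th and 75th percentiles. Keep the median rows for display only, and relabel one of them so that patients exactly at the median are assigned to it.

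The cost is one changed model term and a few extra table entries, with no new data or patients. The downside is the linearity assumption, which should be stated beside the result.

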#### **Secondary objectives:**

Demonstrate the efficacy of an "early-TIPS" strategy to reduce:

- 1/ All-cause mortality rate at Days 42 and 365.
- 2/ Liver related mortality rate at Days 42, 90, 180 and 365.
- 3/ Rebleeding rate at Days 42, 90, 180 and 365.
- 4/ Cumulative incidence of complications of cirrhosis at Day 365.
- 5/ Transfusion requirements at Days 42 and 365.

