#### Early TIPS procedure in experimental arm (Group A):

- TIPS using covered stent will be placed under general anesthesia and with radioscopic guidance by experts.
- The procedure should be performed as soon as possible after randomization and before Day 4.
- Portal pressure should be taken at the time of TIPS insertion, with a goal of hepatic venous pressure gradient of less than 12 mmHg at the end of the procedure.
- Embolization of collaterals will not be authorized in the present study.

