## Glue obliteration procedure in control arm (Group B):

- Filling of varice(s) with tissue adhesive under endoscopic guidance will be initially performed in all patients under general anesthesia. The use of a Doppler EUS will be at the discretion of the practitioner.
- Endoscopic control (and further glue obliteration session if necessary) will be performed in the group B between day-5 and day-8 after the initial bleeding. A new session will then be proposed at days 42+/-7, 90+/-14, 180+/-14 and 365+/-14.
- Endoscopic reports will be systematically collected. The report should specify the topography and size of varices (if possible, a picture will be collected), the type of glue, the volume injected as well as the proportion of Lipiodol.
- In the case of coexistence of esophageal varices, the latter will be systematically treated during the same endoscopic session by band ligation.
- In patients randomized to group B the decision of "salvage TIPS" will be left to the discretion of the investigator and will be then considered as a failure of the endoscopic procedure.
- When placing TIPS for another indication during follow-up in the group B, the patient will be censured at the date of installation of the device.
- In the absence of contraindication, a non-selective beta-blocker treatment will be proposed in the group B according to the recommendations of the Baveno VI Consensus Workshop 2015 (14).

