#### 3.2 Randomization

The trial used a centralized interactive web response system (IWRS) to perform patient allocation (CleanWeb software, Telemedecine Technologies, Boulogne-Billancourt, France). The data manager for the study prepared the randomization schedule for each clinical site participating in the trial. The randomization schedule has the following characteristics: 1. Stratified by center; 2. blocks of size four with equal numbers of patients assigned to the early-TIPS or glue obliteration within each block. The block size was only known by the senior statistician and the data manager of the study.

Only study-certified clinic staff with individually assigned userid/password can access the randomization application. Only participants meeting the inclusion/exclusion criteria according to data entered in the eCRF

system, are listed among the participant IDs eligible for randomization. The date and time of the completion

of the randomization treatment assignment is the time of study entry for each patient.

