#### **Secondary endpoints**

- 1- Survival at Days 42, 90, 180 and 365.
- 2- Incidence of liver related death at Days 42, 90, 180 and 365.
- 3- Incidence of significant rebleeding at Days 42, 90, 180 and 365.
- 4- Cumulative number of packed red blood cells required by each treatment arms.
- 5- Incidence of complications of cirrhosis during the 12-month follow-up.
- any of the complication below
- bacterial infections,
- jaundice,
- ascites.
- spontaneous bacterial peritonitis,
- hepatic encephalopathy,
- hepatorenal syndrome,
- further decompensation.
- 6- Frequency of:
- TIPS technical failure and TIPS complications: thrombosis, heart failure, infection and encephalopathy.

- Technical failure of GO and complications of GO: migration of glue, infection of the site of injection, significant bleeding during the procedure (hospital stay, blood transfusion, 3 g drop in hemoglobin).
- 7- Number of patients lost to follow up at Day 365 in each group
- 8- Change of MELD score between inclusion and Day 180 in each group.
- 9- Number of days spent in hospital in each group during the 12-months follow-up.
- 10- Number of bacterial infections and localizations.

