#### **Definitions**

**Liver-related death** as defined in Asrani et al. (Gastroenterology. 2013;145:375–82.e1–2): death with any of the following causes identified.

Disease category	ICD-10 codes			
Hepatitis C virus	B171, B182			
Other hepatitis	B15, B16, B170, B172, B178, B179, B180, B181, B188, B189, B19, K73			
Primary liver cancer	C22			
Secondary liver cancer	C787			
Esophageal varices	185			
Alcoholic liver disease	K70			
Hepatic failure	K72			
Liver cirrhosis	K74			
Other diseases of liver (toxic, inflammatory, and others)	K71, K75, K76			

**Significant rebleeding** will be defined by Baveno criteria as a recurrent melena or hematemesis resulting in any of the following:

- Hospital admission
- Blood transfusion
- 3 g/dL drop in hemoglobin.

**Bacterial infection:** hospitalization for bacterial infection by the specified time point

**Jaundice**: defined as total bilirubin > 50 μmol/L

Ascites: persistent ascites at the specified timepoint.

**Spontaneous bacterial peritonitis:** defined by an ascitic fluid polymorphonucleated (PMN) cell count of  $\geq 250$ /mm.

**Hepatic encephalopathy** (HE): HE is a brain dysfunction caused by liver insufficiency and portosystemic shunting. HE produces a wide spectrum of nonspecific neurological and psychiatric manifestations. Clinical HE is grading according to the West-Haven criteria.

**Hepatorenal syndrome** (HRS) is essentially a diagnosis of exclusion (i.e., there is an absence of other identifiable causes of renal failure). The hepatorenal syndrome is characterized by the following features in a patient who has established or clinically evident chronic liver disease:

i. diagnosis of cirrhosis and ascites;

- ii. diagnosis of AKI according to ICA-AKI criteria: increase of at least 0.3 mg/dL (26  $\mu$ mol/L) and/or  $\geq$  50% from baseline, within 48 h;
- iii. no response after 2 consecutive days of diuretic withdrawal and plasma volume expansion with albumin (1 g/kg of body weight);
- iv. absence of shock;
- v. no current or recent use of nephrotoxic drugs (non-steroidal anti-inflammatory drugs, aminoglycosides, iodinated contrast media, etc.);
- vi. and no macroscopic signs of structural kidney injury, defined as absence of proteinuria (> 500 mg/d), absence of microhematuria (> 50 red blood cells per high power field) and normal findings on renal ultrasound.

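### The transfusion subgroup counts red cell units past randomisation, so treatment and the primary outcome can help decide which stratum a patient is in

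*SAP*

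**What the plan says.** The subgroup table under the primary composite endpoint (SAP section 6.2) has a row "Red blood cell transfusion during initial hospitalization", split into 0, 1-2 and more than 2 units. Subgroup factors are analysed in a Cox model with treatment, covariate and their interaction. Each stratum gets a hazard ratio, and the row gets an interaction p value.

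The timing is set elsewhere in the SAP:

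- Section 3.2: the date and time of completion "of the randomization treatment assignment is the time of study entry for each patient".
- Section 3.1, group A: "The procedure should be performed as soon as possible after randomization and before Day 4".
- Section 3.1, group B: "Endoscopic control (and further glue obliteration session if necessary) will be performed in the group B between day-5 and day-8 after the initial bleeding".

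Transfusion also appears as an outcome:

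- Section 6.1, Definitions: "Blood transfusion" is one of three criteria that make recurrent melena or hematemesis a significant rebleed, which is a component of the primary endpoint.
- Section 2, Secondary objectives: "Transfusion requirements at Days 42 and 365" is among the quantities that early TIPS is meant to reduce.
- Section 6.1, secondary endpoint 4: "Cumulative number of packed red blood cells required by each treatment arms".
- Section 6.1, secondary endpoint 6, among the glue complications: "significant bleeding during the procedure (hospital stay, blood transfusion, 3 g drop in hemoglobin".

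The baseline list in section 5.3 does not name transfusion. No section limits the row to units given before randomisation.

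**The concern.** A subgroup comparison keeps the protection of randomisation only if stratum membership is settled before treatment is assigned. Here it is not. Eligibility (section 5.1) refers to the 12 hours after the initial endoscopy. TIPS, any early in-hospital rebleed and, for patients still in hospital, the group B control endoscopy all follow randomisation, and units given then count towards the stratum.

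The stratifier also overlaps with the outcome, since an early rebleed that is transfused both counts as a primary event and raises the unit count. If the two arms differ in how many early events they have, they lose and gain events across strata at different rates. Stratum hazard ratios can then differ when the true effect is the same everywhere. A reader would take such a gap to mean that TIPS works better, or worse, after a heavier initial bleed. The encephalopathy and ACLF rows of the same table avoid this because they are fixed at admission.

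**Working it through.** **The plan's figures.** Section 3.3 assumes 12-month failure of 15% (TIPS) and 40% (glue), with 52 patients per group, 80% power, one-sided 0.05 and 10% dropout. A one-sided, continuity-corrected comparison of two proportions gives 47 per group. Then 47 × 1.1 = 51.7, so 52; dividing by 0.9 gives 53. The stated size is reproduced to within one patient. This point does not depend on it; only the two event rates are carried forward.

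**True effect.** HR = ln(1 − 0.15)/ln(1 − 0.40) = 0.1625/0.5108 = 0.318, set equal in every stratum.

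**Closed-form check.** Assume (not in the SAP) that 40% of patients are already above 2 units at randomisation.

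- Per arm: 0.60 × 52 = 31.2 patients with 2 units or fewer, and 20.8 with more than 2.
- Lower-stratum events: 31.2 × 0.40 = 12.48 (glue) and 31.2 × 0.15 = 4.68 (TIPS).
- Upper-stratum events: 8.32 and 3.12.

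Let a fraction f of the lower-stratum glue events, and g of the lower-stratum TIPS events, be in-hospital rebleeds whose transfusion moves the patient to >2 units. In each stratum, HR = ln(1 − TIPS rate)/ln(1 − glue rate).

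Example, f = 0.25 and g = 0.125:

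- Glue: 3.12 events move. Lower rate 9.36/28.08 = 0.333; upper rate 11.44/23.92 = 0.478.
- TIPS: 0.585 events move. Lower rate 4.095/30.615 = 0.134; upper rate 3.705/21.385 = 0.173.
- HR, lower stratum: 0.1436/0.4055 = 0.354. HR, upper stratum: 0.1903/0.6506 = 0.292.

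HR for 2 units or fewer vs more than 2:

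| Fraction moved in the TIPS arm | f = 0.15 | f = 0.25 | f = 0.35 |
|---|---|---|---|
| same (g = f) | 0.31 vs 0.33 | 0.31 vs 0.33 | 0.30 vs 0.34 |
| half (g = f/2) | 0.34 vs 0.30 | 0.35 vs 0.29 | 0.38 vs 0.29 |
| none (g = 0, extreme) | 0.36 vs 0.27 | 0.40 vs 0.25 | 0.45 vs 0.23 |

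**Simulation A.** 400,000 patients per arm. Assumptions: 10-day stay; pre-randomisation strata 30/30/40%; 70% of in-stay events transfused and moved up one or two strata. HRs are for 0 / 1-2 / >2 units.

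| Share of 12-month hazard in the stay, glue / TIPS | HRs by whole-stay count |
|---|---|
| 30% / 30% (proportional hazards) | 0.32 / 0.32 / 0.33 |
| 30% / 20% | 0.35 / 0.33 / 0.30 |
| 30% / 10% | 0.37 / 0.34 / 0.28 |
| 20% / 40% | 0.27 / 0.30 / 0.37 |

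With strata fixed before randomisation, all three HRs are 0.31 in the 30% / 10% case. In the 20% / 40% case they are 0.33 / 0.33 / 0.32.

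**Simulation B.** A separate simulation with a 10-day stay, strata 30/40/30%, 30% of glue failures in the stay, and 75% of in-stay failures moved to >2 units.

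- Proportional hazards: 0.32 / 0.31 / 0.33.
- In-stay HR 0.05: 0.38 / 0.38 / 0.24, against 0.31 in every stratum fixed before randomisation.
- In-stay HR 1.0: 0.17 / 0.17 / 0.56, against 0.34. At N = 104, the interaction test (>2 vs 2 or fewer) is falsely positive in about 16% of trials, against about 3% with pre-randomisation strata.

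**Precision.** Planned events are 52 × 0.40 + 52 × 0.15 = 20.8 + 7.8 = 28.6.

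- Two equal strata: SE of the log ratio of HRs = √[2 × (1/10.4 + 1/3.9)] = 0.84, and exp(1.96 × 0.84) = 5.2.
- Three strata at 30/30/40%, 0 vs 1-2 units: √[2 × (1/6.24 + 1/2.34)] = 1.08, about 8-fold.
- Same split, 0 vs >2 units: √(1/6.24 + 1/2.34 + 1/8.32 + 1/3.12) = 1.01, about 7-fold.

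**The case against.** The strongest reply concerns weight. This is one of nine exploratory subgroup factors, and the primary result does not depend on it. Under proportional hazards, the SAP's default model, the distortion is almost nil. In the closed-form check, 15-35% of 12.48 glue events is only about 2 to 4 patients changing stratum. The larger gaps rest on assumed length of stay, baseline strata, transfused share and a TIPS effect that changes over time, none of which the SAP gives. The 0.17 / 0.17 / 0.56 result and the 16% error rate come from one end of the assumed range. The 30% / 10% case implies an in-stay HR of about 0.11 (0.10 × 0.1625/(0.30 × 0.5108)), which is strong. With three strata, and 10% dropout cutting events to about 26 (46.8 × 0.55), the row is very imprecise anyway. Some transfusion for the initial bleed precedes randomisation, and patients already above 2 units cannot move up. The protocol or eCRF may define the variable more tightly.

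All of this stands as a limit on size and priority. It does not remove the fault. Imprecision does not cancel bias, and proportional hazards is itself an assumption that the SAP plans to test. The row is prespecified with an interaction p value and, as written, uses the whole stay. If only units before randomisation are meant, the SAP should say so.

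**Conclusion.** The point holds. The transfusion row conditions on a variable that can be partly set after randomisation and that overlaps with the primary and secondary outcomes. Its stratum hazard ratios and interaction p value could be biased in either direction, and they cannot be read as effect modification by the severity of the initial bleed.

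Bias is possible, not certain, and its size cannot be known from the SAP. It is close to zero when the same fraction of events moves in both arms. It becomes material when TIPS changes early and late risk to different degrees. The absence of a cut-off is certain from the text; every figure for the bias rests on the assumptions listed with it. The consequence is confined to this one row, which should be corrected before the analysis is run.

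**What to change.** Redefine the row as red cell units transfused from admission to the date and time of randomisation, which section 3.2 already uses as study entry. Report later transfusion only as an outcome. If the timing of transfusions relative to randomisation was not recorded, drop the row.

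The change is one line of SAP wording. Its cost is the need for transfusion dates or times, and the loss of the row if they do not exist. Sample size and the primary analysis do not change.

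Separate editorial points on the same table: the placeholder texts for the shock and no-shock rows are swapped; state where Child-Pugh A patients go, since section 5.1 excludes only scores above 13; and confirm that patients without ACLF have a row, which may simply have been lost when the PDF was read.
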